4.0 OVERVIEW OF STUDY DESIGN/INTERVENTION

4.1 Design

This is a single-center, phase II study to evaluate the efficacy of the 1001 inhibitor, epacadostat, given in combination with the anti-PD1 monoclonal antibody, pembrolizumab, for patients with metastatic and/or locally advanced grade sarcomas.

A total of 30 patients will be enrolled onto the study. Patients will be enrolled onto one of 4 cohorts. Each cohort will enrol a prespecified number of patients with certain sarcoma histological subtype(s). The 4 patient cohorts and the number of patients eligible to enrol per cohort in this study are as follows:

- A) Undifferentiated Pleomorphic Sarcoma (UPS), Liposarcoma (dedifferentiated or pleomorphic liposarcoma), or Myxofibrosarcoma (n=10)
- B) Leiomyosarcoma (n=5)
- C) Vascular Sarcoma Subtypes (including angiosarcomaEpithelioid Hemangioendothelioma (EHE))) (n= 5)
- D) Other (n=10)

This study will be conducted using a one-stage design. Patients will receive the recommended phase II dose (100mg bid) of epacadostat, when administered in combination with pembrolizumab. Epacadostat 100mg will be administered orally, twice daily, continuously for 21 days. Pembrolizumab will be administered at a dose of 200mg every 21 days (±3 days). Treatment with epacadostat and pembrolizumab will start on day 1 of the first cycle. Each cycle will consist of 21 days.

Patients will be evaluated radiographically at baseline, week 8 (+/- 7 days) and every 8 weeks(+/- 7 days) subsequently until week 56 and then every 12 weeks thereafter or as per the discretion of the treating investigator. Response will be assessed using RECIST v1.1 (primary response assessment) and immune-related response evaluation criteria of solid tumors (irRECIST) (secondary response assessment).

All study participants where feasible will undergo mandatory tumor biopsies at baseline and week 7. Optional biopsies at progression will be offered. Biopsies must be collected within +/- 7 days of the originally scheduled timepoint. Serial blood samples will be obtained at baseline, during, and at the end of study treatment.

Study therapy should continue once there is no evidence of progression of disease per RECIST 1.1, no clear clinical deterioration and the patient is able to tolerate the treatment. Treatment beyond progression will be allowed at the discretion of the clinical investigator

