Soluble Factors, Serum	Treatment modulation of serum levels of chemokines, cytokines and other immune mediators by ELISA or other multiplex-based assay methods. Primary analysis includes interferon-gamma and IL-10.	Blood Serum (Weeks 1(before treatment), 4, 7, 13, 22 and off-study)
Characterization of Tumor infiltrating lymphocytes	IHC to assess number and composition of immune infiltrates to define immune cell subsets present within	Tumor biopsy at: Baseline

	tumor before and after exposure to treatment. CD3, CD4, CD8 and FOXP3 will be evaluated. 2. Immune cell phenotyping of freshly isolated TIL to evaluate Treg/Teff ratio (CD8+/FoxP3+ cells) and activations markers (ICOS, PD-1, CD69).	Week 7 Progression (optional)
100- 1, PD-L1 & kynurenine expression by IHC	Qualtek immunohistochemistry- based assay for PD-L1	Tumor biopsy at: Baseline Week 7 Progression (optional)
Tumor Biopsy neoantigen analysis	Fresh frozen tumor biopsy will be utilized for massively parallel whole exome sequencing. Available databases such as SNP effect (http://snpeff.sourceforge.neU will be used to determine which mutations are in coding regions and will affect amino acid sequence. NetMHC and the Immune Epitope Database will be utilized to predict MHC Class I binding and T cell interactions, respectively.	Tumor biopsies at baseline Paired normal peripheral blood mononuclear cells at baseline
T-cell receptor sequencing	Highthroughput sequencing of the variable (3 chain of the T-cell receptor.	Tumor biopsy at: Baseline Week 7 Progression (optional)

Table 5. Study calendar -

	Screening	Cycle 1				2	Cycle 3		Off study		
	Screening	Wk1	Wk2	Wk3	Wk4	Wk5	Wk6	Wk7	Wk8	Wk9	visit ¹
EpacadostatA		Х	X	X	Х	Х	Х	Х	Х	Х	
Pembrolizumab ⁸		Х			Х			Х			
Informed consent	Х										
Pathologic Confirmation at study siteJ	x										
Review of concomitant medications	х	х			х			х			
Review of adverse events		х			х			х			x
Physical exam	Х	Х			Х			Х			Х
Routine laboratory testsc	x	х			х			х			Х
Research blood tests ⁰		х			х			х			Х
Hepatitis B, C and HIV	x										
Pregnancy TestE	Х										Х
ECGF	х								Х		Х
ECHO	х										
CT and/or MRI ⁸	х								х		
Biopsy	Х							Х			

- A. Epacadostat will be administered twice daily, orally, continuously from day 1-21 (inclusive) of each treatment cycle, each treatment cycle consists of 21 days
- B. Pembrolizumab will be administered once at a dose of 200mg, intravenously, on day 1 of cycle **1** and every 3 weeks (±3 days) thereafter

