12.10 Progression-Free Survival (PFS)

PFS is defined as the period from start of study treatment until recurrent or progressive of disease (POD) is objectively documented (taking as reference for progressive disease the smallest measurement recorded on study), death, or date of last study visit involving assessment of disease status.

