12.11 Overall Survival (OS)

OS is defined as the observed length of life from start of study treatment to death or the date of last contact.

12.12 Secondary Response Criteria - Immune-related Response Evaluation Criteria in Solid Tumors (irRECIST)

In 2013, Nishina et al. demonstrated that immune-related response criteria using unidimensional measurements were highly concordant with the bidimensional results of irRC, but with less measurement variability. ⁵⁵ Based on these findings and in order to utilize both the established criteria of irRC and RECIST 1.1, the two systems have been adapted, modified, and combined into the Immune-related Response Evaluation Criteria in Solid Tumors (irRECIST). The adapted irRECIST criteria are modifications to the irRC, incorporating the findings of Nishina et al. and the advantages of RECIST 1.1 while overcoming the shortcomings of each of the other guidelines.

irRECIST

Immune-related RECIST (irRECIST) guidelines according to Bohnsack et al. are presented below.

I. Baseline Assessments in irRECIST

In irRECIST, baseline assessment and measurement of measurable/non-measurable and target/non-target lesions and lymph nodes are in line with RECIST 1.1.

One new definition is added: If a subject has no measurable and no non-measurable disease at baseline the radiologist will assign 'No Disease' (irND) as the overall tumor assessment for any available follow-up time points unless new measurable lesions are identified and contribute to the total measured tumor burden (TMTB). irND is a valid assessment in studies with adjuvant setting where the protocol and study design allow the inclusion of subjects with no visible disease

Follow-up Assessments in irRECIST

A. Follow-up recording of target and new measurable lesions

The key difference in irRECIST is that the appearance of new lesions does not automatically indicate progression. Instead, all measured lesions (baseline-selected target lesions and new measurable lesions) are combined into the total measured tumor burden (TMTB) at follow up. Baseline-selected target lesions and new measurable lesions are

NOT assessed separately. Measurements of those lesions are combined into the TMTB, and one combined assessment provided.

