14.3 Correlative Endpoints Statistical Considerations

The study is not powered to detect specific hypotheses. Due to the small sample size, the correlative studies will be exploratory and hypothesis generating in nature. These analyses will help better identify patients having the potential to benefit from this therapy and aid in designing larger phase III studies.

- I. To evaluate the baseline characteristics of sarcoma tumors (pre-treatment biopsy sample) evaluated in this study including the level of 1001, kynurenine and PD-1/PD-L1 expression, presence of tumor infiltrating lymphocytes (TILs) and tumor antigens, gene expression profile, and the T-cell receptor clonality in tumor-infiltrating lymphocytes (TIL). Descriptive statistics will be used to report the baseline tumor characteristics with respect the level of 1001, kynurenine and PD-1/PD-L1 expression, presence of tumor infiltrating lymphocytes (TIIs) and tumor antigens, gene expression profile, and the T-cell receptor clonality in tumor-infiltrating lymphocytes (TIL).
- II. To assess the potential effect of epacadostat and pembrolizumab on selected biomarker expression measured in pre- and post-treatment tumor tissue and the association between these biomarkers and with clinical outcome, including characterization of 100-1, PD-1/PD-L1, kynurenine expression, tumor infiltrating lymphocytes (Tlls) and tumor antigens, gene expression profiling, characterization of T-cell receptor clonality in tumor-infiltrating lymphocytes (TIL). The pre- and post-treatment measurements will be compared using the paired t-test for each of these biomarkers. The associations with the selected biomarkers, in terms of both the pre-treatment measurement and the difference between pre- and posttreatment measurements, will be evaluated using the two-sample t-test for clinical outcome such as response and clinical benefit, and using survival data analysis (including Kaplan-Meier curve and Cox Proportional Hazards models) for survival outcomes such as progression-free survival and survival. More specifically, Kaplan-Meier curve and Cox Proportional Hazards models will be used for analyzing pretreatment measurement; Kaplan-Meier curve at a landmark time point and Cox Proportional Hazards models allowing for time varying coefficients will be used for analyzing the difference between pre-and post treatment measurements.

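### The Cox model for on-treatment marker change uses time-varying coefficients, which do not address a value first known at the week-7 biopsy and cost precision in a small exploratory analysis

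*Combined protocol and SAP*

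**What the plan says.** Section 14.3, item II, separates two kinds of marker value. For the baseline value the methods are standard: "Kaplan-Meier curve and Cox Proportional Hazards models will be used for analyzing pretreatment measurement". For the change on treatment they differ. The Kaplan-Meier curve is drawn at a landmark, and "Cox Proportional Hazards models allowing for time varying coefficients will be used for analyzing the difference between pre-and post treatment measurements". The landmark belongs to the Kaplan-Meier curve and its time is not given. For the Cox model the section states no landmark, delayed entry or time-dependent covariate, and no form for the time-varying coefficient.

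The timing comes from elsewhere in the document:

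- **Biopsies (section 4.1).** "All study participants where feasible will undergo mandatory tumor biopsies at baseline and week 7". The window is also set there: "Biopsies must be collected within +/- 7 days of the originally scheduled timepoint".
- **Collection times (Table 4, section 10.4.2).** Several tissue assays list "Tumor biopsy at: Baseline Week 7 Progression (optional", so a third, optional sample exists.
- **PFS (section 12.10).** "PFS is defined as the period from start of study treatment until recurrent or progressive of disease (POD) is objectively documented".
- **OS (section 12.11).** "OS is defined as the observed length of life from start of study treatment to death or the date of last contact".
- **First response scan (section 12.1).** Week 8, with a window of one week either side.

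Section 14.3 calls the correlative work exploratory and makes no power claim. It does not say which biopsy supplies the post value, or how patients with an event before the second biopsy are handled.

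**The concern.** Two devices with similar names do different jobs. A time-varying coefficient, b(t), lets the hazard ratio for a fixed covariate change over follow-up. A time-dependent covariate, x(t), lets the covariate take its value only once it is known. The difficulty with an on-treatment change is of the second kind: the clock starts at treatment, but the value does not exist until about week 7. The Kaplan-Meier half of the sentence has a remedy and the Cox half does not.

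Two things are at stake. A progression that precedes the biopsy could be explained by a value measured after it. And a second parameter per marker is spent on a sample that can barely support one. The association between marker change and outcome is one of the stated exploratory objectives (section 2.0, item ii), and section 14.3 says these analyses should inform larger trials.

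**Working it through.** **Plan's own figures.** Section 14.3 gives no event count, hazard ratio or power. The only usable input is the maximum of 30 patients in section 14.1. The design figures attached to it reproduce: with 6 or more responses of 30, the exact binomial gives a type I error of 0.0732 at 10% and power of 0.9234 at 30%, against a stated 0.07 and 92%.

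**Step 1: can an event precede the biopsy?** The biopsy falls in weeks 6 to 8 (7 ± 1) and the first scan in weeks 7 to 9 (8 ± 1). The windows overlap in weeks 7 to 8, so a scan can show progression before the biopsy. Sections 4.1 and 9.4 allow treatment beyond progression, so such a patient may still be biopsied. Two other routes exist: progression found off schedule, and use of an optional progression biopsy as the post value. For OS there is no such route, because nobody is biopsied after death.

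**Step 2: when is the bias nil?** The partial likelihood compares patients only at event times. If no paired patient has an event before the biopsies, every paired patient is in the risk set at every event, whether the clock starts at treatment or at week 7. Simulation agrees: with complete pairs and all events after week 7, the constant-coefficient estimates from the two origins differed by 0.0 in every run.

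**Step 3: how many pairs?** Assume exponential PFS. The number event-free at week 7 is 30 × 0.5^(7/median), and pairs are that number times the paired-biopsy yield. The detectable hazard ratio per SD, counting every pair as an event, is exp[(1.96 + 0.84)/√pairs] for 80% power at two-sided 0.05. The medians and yields are assumptions.

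| Assumed median PFS (weeks) | Event-free at week 7 | Pairs at 60% to 100% yield | Detectable HR per SD |
|---|---|---|---|
| 8 | 16.4 | 9.8 to 16.4 | 2.45 to 2.00 |
| 12 | 20.0 | 12.0 to 20.0 | 2.24 to 1.87 |
| 16 | 22.2 | 13.3 to 22.2 | 2.16 to 1.81 |
| 24 | 24.5 | 14.7 to 24.5 | 2.08 to 1.76 |

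So about 10 to 25 pairs, which is thin even for one coefficient.

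**Step 4: cost of the second coefficient.** Simulated Cox fits with an assumed constant hazard ratio of 2 per SD compare one coefficient with b0 + b1·log(t), tested on 2 degrees of freedom. The first three rows assume a median of 16 weeks after week 7 and censoring at 52 to 104 weeks (800 runs each). The last assumes a median of 2.5 months after week 7 and 12 months of follow-up (1,500 runs).

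| Pairs | Power, one coefficient | Power, time-varying | Loss (points) | SE of log HR, one coefficient | SE at a late time | Ratio |
|---|---|---|---|---|---|---|
| 12 | 47% | 38% | 9 | 0.44 | 0.96 (week 40) | 2.2 |
| 18 | 66% | 57% | 9 | 0.33 | 0.64 (week 40) | 1.9 |
| 24 | 82% | 72% | 10 | 0.28 | 0.53 (week 40) | 1.9 |
| 22 | 74% | 60% | 14 | 0.29 | 0.49 (month 6) | 1.7 |

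In the last row the SE at month 2 is 0.43, a ratio of 1.5. In the first three rows the SE of the time slope itself is 0.53 to 0.99, so a drift in effect could hardly be estimated. Simulation error is about 2 to 4 points.

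**The case against.** The case for leaving the text alone has real weight.

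- **The form of b(t) is open.** A step coefficient, zero before the landmark and constant after, is algebraically the covariate multiplied by an indicator for time after the landmark. That is a correct fit with one parameter. This stands, but the plan does not say it, and the usual reading of the phrase is a smooth departure from proportional hazards. The term may also be a slip for time-varying covariates; the sentence would then still need correcting.
- **The authors saw the timing issue.** They changed methods for the change score and gave the Kaplan-Meier curve a landmark. This also stands; the gap is in the Cox half and in the missing landmark time.
- **Progression biopsies are probably not meant as the post value.** Table 4 lists collection times only. Section 10.4 speaks of paired biopsies at baseline and week 7, and Appendix A labels samples as baseline or on-treatment. Reading the progression sample into the pair is strained, though section 14.3 does not exclude it.
- **Effects may change over time.** Section 9.4 expects some tumours to grow before benefit appears. That is a reason to check proportionality, not to make a two-parameter effect the main model with 10 to 25 pairs.
- **The study claims no power here.** Correct. Exploratory status excuses low power, but not a device that leaves the timing question unanswered.

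**Conclusion.** The point holds as a modest one. The stated Cox method is the wrong tool for a value first known at week 7, and it gives up about 9 to 14 points of power and roughly 1.5- to 2-fold precision at late times. Those sizes rest on assumptions the documents do not supply: 12 to 24 pairs, a hazard ratio of 2 per SD, exponential event times and a log-time form for the coefficient. The direction does not depend on the exact values when the true effect is constant.

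A reader might infer more, in three ways the documents do not support:

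- **That PFS and OS analyses will both use values measured after the event.** For OS this cannot happen. For PFS it needs one of the three routes in step 1, and with a first scan at week 8 few radiographic events should precede the biopsy.
- **That false-positive rates will be badly inflated.** Simulations with 2 or 4 progression biopsies among 26 pairs, each shifted by 1 SD, give about 6% to 9% or 13% to 16% with one coefficient. Coding early failures as unchanged from time 0 gives 14% to 48% for medians of 24 down to 8 weeks. Neither the substitution, the shift nor that coding is in the plan.
- **That the model exhausts the available information.** Most of the overall test's power remains; the main loss is late precision.

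The primary endpoint and its decision rule are untouched.

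**What to change.** In section 14.3, item II, replace the Cox half of the sentence with text to this effect:

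> The change will be analysed in a Cox model with one constant coefficient, either entered as a time-dependent covariate (or with delayed entry) from the on-treatment biopsy date, or fitted from a landmark at the end of the biopsy window (week 8), the same landmark as for the Kaplan-Meier curve, in patients event-free with both biopsies. The number excluded will be reported.

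Add that the post-treatment value is the week-7 biopsy, that progression biopsies are described separately, and that time-varying coefficients serve only to check proportional hazards. The landmark should be week 8 because one at week 7 would precede biopsies taken late in the window.

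The cost is a few sentences and no new data. Section 16.3 describes the study as completed, so the change should be dated and recorded as made after data collection. The downside is small: patients who progress before the landmark or the biopsy leave this model, as they already leave the landmark Kaplan-Meier curve. Delayed entry from the biopsy date keeps those who progress at the first scan after their biopsy, so it is the better choice if early progression is common.

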10.3 Required Laboratory Parameters for Treatment

A new dose of therapy may be initiated provided that the patient meets the following criteria on the day of treatment:

- ANC 1,000/µL
- Platelets> 75,000/μL
- All grade 2 non-hematologic adverse events (except for fatigue, nausea and vomiting, or laboratory values that are not clinically significant) must have resolved to CTCAE grade 1

10.4 - Tumor and blood samples for correlative/companion studies

All patients enrolled on this study will undergo paired biopsies/blood samples for research purposes (correlative/companion studies) where feasible

Blood samples for research purposes will be obtained at week 1 (before treatment), 4, 7, 13, and 22 and at the date of the off study visit (± 3 days). This is detailed in Table 5 (Study calendar). Research blood collection procedures will be performed as outlined in Appendix A.

Biopsies for research purposes will be done at baseline (within 3 weeks of the first dose of epacadostat and/or pembrolizumab) and at Week 7 in all patients enrolled in this study where feasible. Up to 6 cores from each tumor biopsy site should be taken where feasible and safe to do so. An optional biopsy will be offered to all patients at the time of progression. Biopsy procedures will otherwise be performed in accordance with institutional guidelines and the biopsy protocol outlined in Appendix A.

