- C. Routine laboratory tests at screening, day 1 of cycle 1 and then prior to every scheduled treatment visit(± 3 days) thereafter. All routine blood samples should be obtained prior to the daily dose epacadostat and/or pembrolizumab. routine laboratory tests include: cbc with differential, PT/INR and a PTT, comprehensive metabolic panel, magnesium and phosphorus, fT4, TSH, T3, lipase and amylase
- D. Research blood samples will be collected at week 1 (before treatment), 4, 7,13, 22 and at the date of the off study visit(± 3 days)

- E. Serum pregnancy test (Female subject of childbearing potential should have a negative serum pregnancy at screening and within 72 hours prior to receiving the first dose of both study drugs and at the off study visit.)
- F. An ECG will be performed at baseline, week 8, every 8 weeks subsequently((± 1 week window) and at the off study visit((± 1 week window)
- G. Standard Imaging studies will be performed at baseline, week 8 and every 8 weeks subsequently (± 1 week window) until 56 weeks, and then every 12 weeks thereafter or as per the discretion of the treating investigator and will include CT of chesUabdomen/pelvis and MRI of the affected area if deemed necessary by the study investigator.
- H. Optional biopsy at progression.
- I. The off study visit will take place 30 days(+/- 7 days) after the last dose of study therapy
- J. Pathologic confirmation of the presence of sarcoma at the study site may take place during or before the screening period.

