- III. To evaluate associations between selected biomarkers measured in serial peripheral blood over time with clinical efficacy, including immunophenotyping and functional analyses, evaluation of serum levels of chemokines, cytokines and other immune mediators, and characterization of T-cell receptor clonality in peripheral blood.
 - Summary statistics will be used to for describing changes across time. In addition the time course of biomarker measurements will be investigated graphically, by summary plots or individual patient plots; their trends over time will be categorized either by visual inspection (if there are clear trend groups such as monotonically increasing or

monotonically decreasing) or by pattern recognition methods such as K-means clustering. The associations with the observed trend in selected biomarkers analyzed will be evaluated using categorical data analysis (including Fisher's exact test and logistic regression) for clinical outcome such as response and clinical benefit, and using survival data analysis (including Kaplan-Meier curve and Cox Proportional Hazards models) for survival outcomes such as progression-free survival and survival.

IV. To evaluate the association between baseline tumor mutational burden and neoantigen production with clinical efficacy of the study therapy.

The associations with baseline tumor mutational burden and neoantigen production will be evaluated using categorical data analysis (including Fisher's exact test and logistic regression) for clinical outcome such as response and clinical benefit, and using survival data analysis (including Kaplan-Meier curve and Cox Proportional Hazards models) for survival outcomes such as progression-free survival and survival.

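### Section 14.3 item III groups patients by blood-marker trend without a landmark, so comparing monotone patients with the rest can make an unrelated marker appear to predict poor PFS

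*Combined protocol and SAP*

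**What the plan says.** Section 14.3 item III deals with markers in serial peripheral blood. After summary statistics and plots, patients are grouped by trend. On the first route, "their trends over time will be categorized either by visual inspection (if there are clear trend groups such as monotonically increasing or". After a page break the sentence goes on to the opposite trend and to the second route: "monotonically decreasing) or by pattern recognition methods such as K-means clustering". The groups are then related to response by Fisher's exact test and logistic regression, and to time-to-event outcomes "using survival data analysis (including Kaplan-Meier curve and Cox Proportional Hazards models) for survival outcomes such as progression-free survival and survival".

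Item III does not say which samples define a trend, how many are needed, or where patients with no clear trend go. It names no landmark.

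Four other places bear on this:

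- Section 10.4: research blood is "obtained at week 1 (before treatment), 4, 7, 13, and 22 and at the date of the off study visit".
- Table 5, note I: "The off study visit will take place 30 days(+/- 7 days) after the last dose of study therapy".
- Sections 12.10 and 12.11: "PFS is defined as the period from start of study treatment until recurrent or progressive of disease" and "OS is defined as the observed length of life from start of study treatment to death".
- Section 14.3 item II, for the pre/post difference in tumor tissue: "Kaplan-Meier curve at a landmark time point and Cox Proportional Hazards models allowing for time varying coefficients will be used".

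Section 14.3 describes the correlative work as exploratory and not powered. It also expects the work to help identify patients who may benefit and to aid phase III design.

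**The concern.** A trend group is known only after treatment has run for some time, yet item III uses it as if it were known at treatment start. The length of the series depends on the outcome as well. Section 1.0 has treatment repeated until progression or unacceptable toxicity, so patients who progress early give fewer samples, and a short series is more likely to go all one way by chance.

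If monotone patients are set against everyone else, short PFS puts patients into the monotone group even when the marker has nothing to do with outcome. A drift shared by all patients on treatment can have a similar effect on slope or cluster groupings, because the length of the series then shapes the apparent trend.

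An error of this kind runs in one direction. It would point to a marker of poor outcome, and repeating the same analysis in another study would reproduce it.

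**Working it through.** Item III states no figure of its own to reproduce. The one design calculation in Section 14, for the primary endpoint, does reproduce (at least 6 responses in 30: type I error 0.073, power 0.923) and is not at issue.

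**Inputs from the documents.** 30 patients (Section 14.1); sample times (Section 10.4); off-study visit about 30 days after the last dose (Table 5); scans every 8 weeks to week 56, then every 12 (Section 4.1); PFS from treatment start (Section 12.10).

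**Assumptions, not in the documents.** Exponential PFS with median 12–16 weeks, detected at the next scan; a marker independent of PFS; a log-rank test at 5%; at least 2 patients per group.

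**Step 1, samples per patient.**

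- Stops at the first scan: weeks 1, 4, 7 and off study = 4.
- Stops at the second scan (week 16): weeks 1, 4, 7, 13 and off study = 5.
- Treated past week 22: weeks 1, 4, 7, 13, 22 and off study = 6.

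**Step 2, chance that k samples look monotone.**

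- Random walk, all k − 1 steps in one direction: 2 × (1/2)^(k−1). This is 1/4 for k = 4, 1/8 for k = 5 and 1/16 for k = 6, so the earliest progressors are four times as likely to be called monotone as the longest-treated patients.
- White noise, 2/k!: 8.3%, 1.7% and 0.3%. The gradient is steeper, but few patients qualify.

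**Step 3, simulated false positives on PFS, monotone versus rest, random-walk marker, among analysable data sets.**

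| Setting | Rate |
|---|---|
| Off-study sample included, nobody treated past progression | 27–32% |
| 40% continue one 8-week interval past progression | 20–25% |
| All continue one interval | 11–15% |
| Shuffled group labels (40% continuing) | 5–6% |
| Week-7 landmark | 4–7% |

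Separate runs differ by one to two points from these ranges. Between 92% and 100% of the false positives had the monotone group doing worse. At 40% continuing, mean PFS in monotone patients versus the rest was 15.6 versus 22.6 weeks (median 12) and 19.8 versus 28.5 weeks (median 16).

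**Step 4, the denominator.** The monotone group holds about 4 of 30 patients. At 40% continuing, 1,335 and 1,266 of 1,500 trials were analysable for medians 12 and 16. Over all trials the random-walk rates are 0.207 × 1,335/1,500 = 18% and 0.254 × 1,266/1,500 = 21%. With noise added to the marker, the rate over all trials is about 11–12%; with white noise it is 3–6%.

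**Step 5, other comparisons at 40% continuing.**

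- Increasing versus decreasing: 3–6%, evaluable in only 232–451 of 1,500 trials.
- Slope sign without drift: 6–7%. K-means without drift: 6%.
- Response by Fisher's exact test: 1–2%.
- Shared drift of 1 SD, four assumed shapes: 7–13% for slope sign and 5–26% for K-means.
- OS, monotone versus rest: 11–12%. This assumes survival after progression with a median of 40 weeks, censored 52 weeks after treatment ends.

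**The case against.** **The inflated comparison is not named in the plan.** The groups it names are increasing and decreasing, and that comparison is near nominal. This stands: monotone versus rest is one reading, left open because the plan does not place patients with no clear trend. A reader might infer that every grouping under item III is biased. Step 5 does not support that.

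**Visual grouping applies only if clear groups appear.** Four monotone patients in 30 may not count as clear groups. Requiring at least 5 left 19–30% of random-walk trials usable, with 5–8% rejections over all trials. Among the usable trials the rate was still about 27%. The condition makes the error rarer but does not remove it.

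**A noise-free random walk is a favourable choice for the concern.** This stands on size. With added noise or moderate autocorrelation the monotone group fell to 1.3–1.7 patients and 40–50% of trials were usable. With white noise it was 0.6–0.8 patients and 11–19%. Rates within usable trials stayed at 25–49%, but on groups of 2–3 patients.

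**Item III sets no significance level.** That is so, and 5% is only a yardstick. The distortion does not depend on it: with median PFS 16 weeks and nobody continuing past progression, the large-sample hazard ratio for an unrelated marker was 1.54, against 0.97 under a week-7 landmark.

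**A week-7 landmark has a price.** With three samples, 2 × (1/2)^2 = 1/2 of null random-walk patients look monotone. This stands: week 7 is a choice, and the documents do not require it.

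A reader might also infer a rate of 42–47%. That figure arises only if on-treatment samples alone are used, and the plan schedules an off-study sample, so it does not describe the plan.

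**Conclusion.** The gap is real and the concern holds in a limited form. Followed as written, item III can give a biased association with PFS if monotone patients are compared with the rest, or if the marker drifts on treatment. The direction follows from the sampling schedule; the size rests on assumptions about PFS and marker behaviour that the documents do not supply.

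Treatment past progression, which Sections 4.1 and 9.4 allow, weakens the effect without abolishing it. With noisy markers the usual result would be a group too small to test, not a false finding. The response analysis in item III is not inflated, and the primary and secondary endpoints are untouched. A reader might take this as casting doubt on the trial's efficacy conclusions; nothing in the documents supports that. It is a worthwhile correction to an exploratory analysis.

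**What to change.** Extend item II's landmark to item III:

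- Prespecify one landmark common to all patients.
- Define trend groups only from samples up to the landmark, and leave the off-study sample out.
- Include only patients still at risk (progression-free for PFS, alive for OS) and count PFS and OS from the landmark.
- State how patients with no clear trend are grouped.
- Use later samples descriptively or as time-dependent covariates.
- For consistency, use the same samples for every patient in the response analysis.

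It is the landmark that has to carry over. Item II's time-varying coefficients alone would not change when the group becomes known.

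Week 7 is one workable choice. Counting weeks as in Table 5, the week-7 draw falls on day 43 ± 3, and a week-8 scan (day 50) taken 7 days early also falls on day 43, so the landmark should lie after day 46. About 27–28 of 30 patients would remain; the lower figure assumes that 20% of progressions before week 7 are called clinically. A week-13 landmark gives four samples but keeps only 19–21 patients, with about 5 in the monotone group.

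The cost is fewer time points per patient and the loss of patients with earlier events. Section 16.3 says the study has been completed, so the change is to wording, code and reporting only. If blood results have already been related to outcome, the landmark should be reported as chosen afterwards.
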